5.3.7.8 Stratification: ISI severity screening score and current hormone therapy status (yes/no)

5.4 An email confirmation of registration will be sent from the URCC NCORP Research Base.

5.5 Registration and randomization of participants will occur when an entire cohort has been consented. A cohort consists of a yoga group, a CBT-I group and a health education group at a single NCORP location. All participants are registered at the same time. The minimum number of participants to comprise a cohort is 15 and the maximum is 30. The NCORP must notify the URCC when the final participant in a cohort is being consented, and provide the total number of participants enrolled to that cohort, the institution's CTEP ID, and the date of the first day of the baseline week. The Research Base requires a 24-hour turn-around time to open the registration site. The NCORP site must then register the entire cohort of participants within 24 hours and will receive the randomization assignment for each participant at that time. **NCORP coordinators will know the randomization assignments; however participants are not to be notified of their randomization assignments until they have completed all baseline assessments.** The participants randomized to each of the three conditions will all participate in the intervention they are assigned together as a group and the sessions will only contain study participants. (Note: The URCC has successfully used this method of randomization in previous studies including U3905 (the prior yoga study), U2991 and U9994 where cohorts were randomized to treatments delivered using group formats.) Participant cohorts will be recruited at each NCORP and then randomized; this will allow for statistical analyses by site.

- 5.6 A total enrollment of 720 participants (accounting for 30% of participants providing non-evaluable data) is planned as follows:

Group	N	Evaluable
YOCAS	240	168
CBT-I	240	168
Health Education	240	168

- 5.7 Randomization will be stratified by ISI severity score obtained during the screening process (ISI score of 10-18 = “moderate” and 19-28 = “severe”) and hormone therapy (two levels: yes/no). In addition, participant cohorts will be recruited at each NCORP and then randomized; this will, in turn, allow for statistical analyses by site.
- 5.8 The three study arms are as follows:
- Arm 1 = The standard YOCAS® intervention  

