once a week for 90 minutes over an 8 week period. CBT-I instructor qualifications are documented in a resume or CV and submitted to the Research Base for approval.

6.5 **Health Education Control Group:** This group will receive a survivorship health education intervention (equally matched to YOCAS® for time and attention) which is based on the American Society of Clinical Oncology cancer survivorship educational recommendations and a booklet entitled “Cancer Survivorship Next Steps for Patients and Their Families.” (See the health education booklet.) The intervention is delivered by community health educators with a minimum of a Bachelor’s degree in a health-related field or Registered Nurse certification, and a year of experience working in a clinical oncology setting with patients. This intervention is delivered 2 times a week for 75 minutes per session over 4 weeks. Health professional qualifications are documented in a resume or CV and submitted to the Research Base for approval.

6.6 The participants will all participate in the treatment they are assigned together as a group (1 group for each study arm condition) and the treatment sessions will only contain study participants. Participants will not be charged for any of the treatment sessions.

6.6.1 Each participating NCORP will be responsible for finding suitable yoga, CBT-I and health education instructors.

The study PI, [name], along with members of the research team, will be available to assist NCORPs in selecting appropriate instructors. Each instructor will be required to provide the following:

- copy of his/her resume or curriculum vitae
- documentation of his/her Yoga Alliance or International Association of Yoga Therapists (IAYT) instructor training and certification status, CBT instructor training/experience, or health educator instructor training/experience in a clinical oncology setting.
- personal liability insurance information
- in order to be paid as a study consultant, the instructor will complete
  - an IRS W-9 form
  - a University of Rochester Acceptance form to follow the terms and conditions of working with the University

Additionally, the instructors will sign an Adherence Statement promising to follow the yoga, CBT-I and health education interventions exactly as outlined in the clinical protocols provided.

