The NCORP site will submit these materials to the Research Base ([name]) for review by [name] and members of the research team to approve the yoga, CBT-I and health education instructor for consultation and for teaching the interventions.

Each instructor will also be required to complete a training session with Research Base staff under the direction of [name], prior to final approval as a study instructor.

A decision regarding approval of the instructor will be made within two weeks of providing all the necessary materials and fully completing training.

All instructors will be paid directly as consultants by the URCC NCORP Research Base. Instructors must submit an invoice to the Research Base within 7 calendar days of completing the series of 8 intervention sessions for processing. Instructors will be paid a flat fee of \$1200.00 per cohort to teach all 8 sessions and includes all preparation and travel time. Instructor invoices should be sent to: [name] at [name].

- 6.6.2 Details and logistics on where the yoga, CBT-I and health education sessions will be conducted, obtaining props, meeting rooms and specifics regarding participant transportation will be individualized by each NCORP site.

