- 6.8 **Intervention Quality:** The exact same procedures used to ensure quality and fidelity and to prevent drift that were used in the previous yoga study, U3905, will be used in this trial, except we will use videotaping to ensure proper class content rather than independent observations. The interventions will be delivered by professionally qualified instructors hired and vetted by [name] and members of the research team. All instructors will receive extensive training regarding the information to be taught. Training updates will be provided minimally every year for instructors and NCORP site staff. [name] and her staff will be available to answer questions at all times. Coordinators will be required to videotape the third class in each condition and send the videotape to the URCC NCORP Research Base by the end of the next business day. Tapes will be reviewed within 3 business days of receipt by qualified staff under the direction of [name]. Immediate feedback will be provided to the instructor and NCORP site staff so that corrections can be made if necessary. If at any time a coordinator or staff member realizes the intervention protocols are not being followed properly, the Research Base and study P.I. ([name]) must be notified immediately. Video recordings will be uploaded via the research base's secure encrypted Box data upload system. Once URCC has reviewed the video recordings and given authorization, the sites must destroy them.
- 6.8.1 **Assessment Data Quality:** The coordinators must submit all baseline data from one individual in each of the three arms by the 3rd work day post baseline. This includes paperwork, fitness assessments, and actigraphy. Data are either uploaded or emailed to URCC. The Research Base will review and give the sites feedback so that corrections can be made if necessary. Once the site has downloaded the actigraph data they must immediately give the actigraphs back to the appropriate participants so they have them before the mid-intervention assessment.

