Hypothesis 2 = YOCAS® vs. health education). **The response will be post-treatment ISI total score.** The model fixed effects will be Group and Baseline ISI. NCORP Site will be included as a random effect. The REML method will be used to estimate the random effect variance components. If the NCORP Site variance component is significant, the fixed effects will be tested using F tests with the Kenward-Roger degrees of freedom adjustment. If the NCORP Site variance component is not statistically significant, we will use ordinary least-squares estimation and F-Tests for testing the fixed effects. The mean difference between groups with associated 95% confidence intervals will be estimated using the appropriate contrasts. An alpha level of 0.025 will be used to adjust for multiple comparisons. Additional follow-up analyses will include NCORP site and cohort as covariates and examine possible interactions.

- 10.7.2 **Secondary Aim 2 Analyses:** To examine if YOCAS® is effective for improving **objective symptoms of insomnia** (sleep latency, sleep efficiency, wake after sleep onset, sleep duration, and daytime napping via actigraphy) and **global sleep quality impairment** (PSQI total) compared to CBT-I and a health education control, we will use the same methods as for Primary Aim 1 with no multiple comparison adjustments.

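### The primary model and the power calculation ignore the closed, instructor-led treatment groups: with any positive within-group ICC, either the 0.025 error is exceeded or a valid test falls short of 80% power

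*Combined protocol and SAP*

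**What the plan says.** On delivery, section 5.5 forms cohorts at a single location: "The minimum number of participants to comprise a cohort is 15 and the maximum is 30". After individual 1:1:1 randomization, "The participants randomized to each of the three conditions will all participate in the intervention they are assigned together as a group", in sessions open only to study participants. Section 6.6 confirms one group per arm. Section 6.6.1 makes the instructors local: "Each participating NCORP will be responsible for finding suitable yoga, CBT-I and health education instructors". They receive a flat fee "per cohort to teach all 8 sessions and includes all preparation and travel time".

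On analysis, section 10.7.1 specifies: "The model fixed effects will be Group and Baseline ISI. NCORP Site will be included as a random effect". Group here means study arm, not the class. A fallback removes the random effect: "If the NCORP Site variance component is not statistically significant, we will use ordinary least-squares estimation and F-Tests for testing the fixed effects". Cohort appears once, after the primary test: "Additional follow-up analyses will include NCORP site and cohort as covariates and examine possible interactions".

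On power, sections 10.1 to 10.2.2 use an SD of 4.6, a baseline-to-post correlation of 0.576, 168 evaluable per arm and alpha 0.025. They mention no group size, ICC or design effect.

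**The concern.** People who share a room, an instructor and eight sessions may have correlated outcomes. These groups are nested within arm, so variation between them goes straight into the arm difference. Site variation does not, because every cohort runs all three arms at one location and a site effect is common to them. A cohort main effect is shared across arms in the same way. Only a cohort-by-arm term represents the class, and the deciding model has none.

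If outcomes within groups are positively correlated, one of two things follows. If the model stays as written, its standard error is too small, and YOCAS is declared non-inferior to CBT-I, or superior to health education, too often when that is false. If the model is corrected, the trial has less than the stated 80% power. These are alternatives: they do not both occur at full size in the same analysis.

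**Working it through.** **Reproducing the plan's figure.** Inputs from section 10.2.1: SD 4.6, correlation 0.576, margin 1.15, 168 per arm, one-sided alpha 0.025.

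- Baseline-adjusted SD = 4.6 × √(1 − 0.576²) = 3.760
- SE of the arm difference = 3.760 × √(2/168) = 0.410
- Power = Φ(1.15/0.410 − 1.96) = 80.0%

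For Hypothesis 2 (two-sided 0.025), the difference detectable with 80% power is (2.241 + 0.842) × 0.410 = 1.265, which the plan rounds to 1.3. Both figures treat observations as independent.

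**Group size.** Cohorts of 15 to 30 split three ways give 5 to 10 enrolled per group. After the planned 30% loss this is m = 3.5 to 7 evaluable. The number of groups per arm is 720/15 = 48 down to 720/30 = 24.

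**Effect of clustering.** The ICC, on the baseline-adjusted scale, is my assumption: 0.01 to 0.10, equal in the two arms compared. With equal groups:

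- Design effect DE = 1 + (m − 1) × ICC
- Hypothesis 1 one-sided error of an unadjusted test = 1 − Φ(1.96/√DE)
- Hypothesis 1 power of a valid test = Φ(1.15/(0.410 × √DE) − 1.96)
- Hypothesis 2 two-sided error = 2 × (1 − Φ(2.241/√DE))

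Each range runs from m = 3.5 to m = 7.

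| ICC | DE | H1 error, unadjusted | H1 power, valid test | H2 error, unadjusted |
|---|---|---|---|---|
| 0.01 | 1.025–1.06 | 0.026–0.029 | 79–78% | 0.027–0.030 |
| 0.02 | 1.05–1.12 | 0.028–0.032 | 78–75% | 0.029–0.034 |
| 0.05 | 1.125–1.30 | 0.032–0.043 | 75–69% | 0.035–0.049 |
| 0.10 | 1.25–1.60 | 0.040–0.061 | 71–60% | 0.045–0.076 |

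At a middle group size of 5.25 and ICC 0.02, Hypothesis 1 error is 0.030 and valid power 77%. With group-level degrees of freedom (2 × 48 − 2 = 94 down to 2 × 24 − 2 = 46), valid power at ICC 0.05 is 74–67%. The detectable difference for Hypothesis 2 at ICC 0.05 is 1.265 × √DE = 1.34–1.44.

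**Simulation of the plan's two branches.** There were 10,000 trials per cell at a true difference of 1.15, with groups of 4, 5 or 7, one cohort per site and an assumed site variance of 5%. The entries are one-sided error.

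| ICC | Site as a block | Ordinary least squares |
|---|---|---|
| 0 | 0.024–0.025 | 0.021–0.022 |
| 0.02 | 0.030–0.034 | 0.026–0.030 |
| 0.05 | 0.034–0.044 | 0.029–0.039 |
| 0.10 | 0.050–0.065 | 0.043–0.058 |

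The inflation appears in both branches, so the switch to least squares is not its source. A test on cohort-by-arm group means gave 0.023–0.027 in every cell. A separate simulation, with 40,000 trials per setting and one or two cohorts per site, agreed: at 7 per group and ICC 0.05 it gave 0.041 with least squares and 0.043–0.044 with site as a block.

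**The case against.** The strongest objection is that the size is assumed. No ICC is given, and nothing in the documents makes 0.05 or 0.10 more plausible than 0.01, where the loss is one to two points of power. The worst figures also need every cohort at its maximum of 30. This stands, and it is why the finding is conditional.

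Three points refine the size:

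- The 168 are fully evaluable participants, who also need PSQI, diary and actigraphy data (section 10.1). The primary model needs only ISI, so more may contribute. If, as an assumption, 85% supplied ISI data (204 per arm, m = 4.25–8.5), valid power would be 85–82% at ICC 0.02 and 82–75% at 0.05. The error would then be slightly larger, at 0.029–0.034 for ICC 0.02.
- The ICC may differ between arms. With 0.05 in one arm and zero in the other, simulated least-squares error was 0.029–0.036.
- In the least-squares branch, simulated error is somewhat below the closed-form figures; with site as a block it is slightly above.

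The plan also has partial safeguards. Instructors are centrally trained and approved, and section 6.8 adds a fidelity check: "Coordinators will be required to videotape the third class in each condition". The follow-up analyses may examine interactions. These can reduce instructor variation or reveal group dependence. They do not remove correlation among people treated together, and they do not change the test that decides the trial. The assumption checks in section 10.6.1 do not cover independence.

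**Conclusion.** The concern holds. The omission is certain from the text. Its size depends on an ICC that the plan neither states nor allows for. At 168 per arm, the 80% for Hypothesis 1 has no slack for any positive ICC; Hypothesis 2 has only the slight slack from rounding 1.265 up to 1.3. The effect is modest at ICC 0.01 to 0.02 and material from about 0.05. These figures assume equal groups and an equal ICC in both compared arms. Unequal groups would lower valid power a little further, and an instructor who teaches several cohorts would add correlation not counted here. The error matters most for Hypothesis 1, where a standard error that is too small favours a false claim of non-inferiority to CBT-I. Sections 10.7.2 and 10.7.4 reuse the primary methods, so the gap carries into those comparisons. This should be fixed before analysis.

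**What to change.** **Section 10.7.1.** Add a random effect for the arm-specific treatment group (cohort by arm), plus instructor or site-by-arm where one instructor teaches several cohorts. Keep it whatever its p-value, use Kenward-Roger degrees of freedom, and state that the least-squares fallback does not remove it.

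**Sections 10.1 and 10.2.** State that 80% power for Hypothesis 1 applies at 168 evaluable per arm with zero group ICC. Tabulate power for both hypotheses over a range such as 0.01 to 0.10, with the assumed group size.

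**Cost.** This takes SAP wording and a power table. Cohort, arm and site are already recorded. An instructor identifier is not listed in the section 11 records table and may have to be recovered from attendance logs or invoices. Confidence intervals will be wider and the stated power lower. Wording does not restore lost power: holding 80% for Hypothesis 1 by enrolment alone would take about 720 × DE participants, which is 756–807 at ICC 0.02 or 810–936 at 0.05. The sponsor may instead accept and state the lower power.

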## 10.0 Data Handling and Statistical Considerations

---

- 10.1 **Sample Size and Statistical Power:** Allowing for 30% of participants who may not provide complete data (as in our prior study), we will need to enroll a total of 720 participants to have 504 fully evaluable participants (168 evaluable in each of the three study arms). Fully evaluable participants is defined as having completed the On Study/ Participant Interview and the Clinical Record Information (baseline), the ISI, PSQI, Daily Diaries, and actigraphy (baseline and post-intervention assessments) for primary and secondary endpoints. With 504 fully evaluable participants, will have 80% power at a 0.025 significance level to test our hypotheses. We will use a significance level of 0.025 to control for type I error because two hypotheses (i.e., 1 inferiority [yoga vs. CBT-I] and 1 superiority [yoga vs. health education]) will be tested in our primary aim. *[Note: We will reimburse survivors for participating in this study in an effort to decrease attrition and data loss.]*
- 10.2 **Power for Primary Aim 1:** The two primary hypotheses to be tested in our primary aim include: (1) YOCAS® will be as effective as CBT-I, and (2) YOCAS® will be more effective than the health education control.
- 10.2.1 **Power for Hypothesis 1:** Based on baseline data from our previous phase III RCT examining the effects of yoga on insomnia and data from Savard and Morin, we assume an ISI standard deviation of 4.6. Since half a standard deviation is commonly accepted as appropriate for estimating a clinically important change, we regard a difference of 2.3 (half a standard deviation) between YOCAS® and CBT-I as nontrivial. Following the same methods as Garland and colleagues, we set the non-inferiority margin to 1.15 (half of the 2.3 difference). We will test the **null** hypothesis that the difference in mean change on the ISI between YOCAS® and CBT-I is greater than 1.15; that is, YOCAS® is *inferior* to CBT-I. Rejection of the null hypothesis means that YOCAS® is as effective (*non-inferior*) as CBT-I. Using ANCOVA to estimate differences in mean change between YOCAS® and CBT-I, a correlation of 0.576 (from our prior study), and a sample of 168 subjects per group, we will have sufficient (80%) power to detect non-inferiority using a margin of 1.15 at  $p = 0.025$ .

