- 10.6.2 **Missing Values.** Every effort will be made to facilitate participants' completion of questionnaires and provision of actigraphy and physical function data, and blood. In the event of missing data, the reasons for missing data will be recorded and tabulated according to treatment group. Some missing data are inevitable. Under the missing at random (MAR) assumption, we will use multiple imputation to obtain unbiased estimates of key parameters. If data are suspected to be missing not at random (MNAR), a sensitivity analysis using the methods of Liublinska and Rubin (2014) will be run to determine the impact on results. If the estimates are similar to the ones obtained from the simpler analysis of only complete cases, we will report the complete-case analysis results.
- 10.7 **Statistical Analyses:**
- 10.7.1 **Primary Aim 1 Analyses:** To determine if YOCAS® is as effective as CBT-I and more effective than health education for improving **insomnia (ISI total)**, two separate analyses will be performed, each aimed at estimating the difference between arms in mean change from baseline with associated confidence intervals. The comparison of YOCAS® to CBT-I is a non-inferiority hypothesis with a one-sided alpha, and the comparison of YOCAS® to the health education control is a traditional null hypothesis of no difference with a two-sided alpha. See the Statistical Power section for more details. A linear mixed effects ANCOVA will be used to assess the statistical significance of the differences in mean changes from baseline for the two groups (Hypothesis 1 = YOCAS® vs. CBT-I;

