- 10.7.3 **Secondary Aim 3 Analyses:** To examine if YOCAS® and CBT-I are effective for **maintaining improvements in insomnia at 3 and 6 months post-intervention** compared to a health education control, we will perform a longitudinal analysis using the ISI total score at all five time points as the response. The fixed effects will be Time, Group (all three in this analysis), and Time by Group interaction. Within-subject random effects will initially be modeled assuming an unstructured covariance matrix, but will be simplified after inspection of the estimated covariance structure (e.g., compound symmetry). If NCORP Site variance in the primary analysis is statistically significant at the 0.05 level, it will be included as an additional random effect, independent of the within-subject random effects. REML estimation will be used. Fixed effects will be tested using F tests with the Kenward-Roger degrees of freedom adjustment. The impact of group on the time trajectory of insomnia will be tested via the Time\*Group interaction. Least-squares means for each Time and Group combination will be plotted to visualize and understand the time trajectories of insomnia. Differences in time trajectories between the three groups will be tested with no adjustments for multiple comparisons.

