- 10.7.4 **Exploratory Mechanistic Aim 4 Analyses:** To explore whether YOCAS® is effective for improving **circadian activity rhythms (24 and 12 hour amplitudes and acrophases via actigraphy), physical function (i.e., cardiopulmonary [6-min. walk] and muscular function [dynamometry]), and inflammation (IL-6, IL-8, IL-10, IL-1 $\beta$ , IFN- $\gamma$ , & TNFR1 via standardized ELISAs and multiplexes)** compared to CBT-I and a health education control, we will use the same analytical methods as for Primary Aim 1 to assess changes in the estimated parameters of the two-oscillator (12 and 24 hours) cosinor model and the Hill function model. These parameters include **Mesor (M), Amplitude (A1) and Acrophase (Phi1) for the 24-hour oscillator and Amplitude (A2) and Acrophase (Phi2) for the 12-hour oscillator.** Estimates will be from the log-transformed activity counts using nonlinear regression. Degree of rhythmicity will be assessed with the Fisher-transformed model multiple correlation. We will also fit single-oscillator models (24-hour Mesor, Amplitude, and Acrophase) for comparison with other published studies. The time participants woke up in the morning and fell asleep in the evening will be extracted from weekly diaries. We will apply the same methods as for physical function and inflammation outcomes; inflammatory biomarkers will be log-transformed as needed.
- 10.7.5 **Exploratory Mechanistic Aim 5 Analyses:** To explore **whether changes in physical function, circadian rhythm and inflammation mediate the effect of YOCAS® on insomnia,** we will use separate mediation analyses performed on pre-post ISI change scores (CS) and the above outcomes as potential mediators. Path analysis will be used, where the intervention affects CS, the intervention affects the mediator, and the mediator, in turn, affects the CS. We will also use structural equation modeling. Mediation will be assessed via indirect effect estimation using bootstrap-based 95% confidence intervals. Latent variables will be introduced into the model for multiple measures of a common entity (e.g., cytokines for inflammation). If multiple measures are weakly correlated, we will split them

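### Hormone therapy stratifies the randomisation but is left out of the primary and secondary models, at a small cost in precision

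*Combined protocol and SAP*

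**What the plan says.** Registration collects the two stratifiers (Section 5.3.7.8): "Stratification: ISI severity screening score and current hormone therapy status (yes/no". Section 5.7 confirms the second as "hormone therapy (two levels: yes/no".

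The models are as follows.

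- **Aim 1 (10.7.1).** "The model fixed effects will be Group and Baseline ISI", plus a random effect for NCORP site. The only further covariates are in secondary follow-up work: "Additional follow-up analyses will include NCORP site and cohort as covariates and examine possible interactions".
- **Aim 2 (10.7.2).** The Aim 1 methods are reused.
- **Aim 3 (10.7.3).** "The fixed effects will be Time, Group (all three in this analysis), and Time by Group interaction". Site is added only if its variance component was significant in the primary analysis.
- **Aim 4 (10.7.4).** "we will use the same analytical methods as for Primary Aim 1".
- **Aim 5 (10.7.5).** The path model links intervention, mediator and ISI change score, and lists no covariates.

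Within Section 10, hormone therapy is named once, in 10.7.6, in a list of variables whose interrelationships will be explored to generate hypotheses. The power calculation in 10.2.1 rests on "a correlation of 0.576 (from our prior study), and a sample of 168 subjects per group" and takes no account of it. Section 10.6.2 says "we will use multiple imputation to obtain unbiased estimates of key parameters" but does not list the variables in the imputation model.

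**The concern.** Stratifying on a factor forces it to be nearly equal across arms. If the factor also predicts the outcome, the estimated treatment difference varies less from trial to trial than a model without the factor assumes. The factor's variance stays in the residual, so the reported standard error is too large and the confidence interval too wide. The estimate itself is not biased.

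The error is therefore in the safe direction. What is at stake is precision in the two primary comparisons. The non-inferiority test is the tighter one, because it is planned at 80% power with no reserve.

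A second, weaker consideration is the 30% of participants expected to be non-evaluable (Sections 5.6 and 10.1). If loss is random, any imbalance on hormone therapy among completers is chance. Bias would require loss that depends on hormone therapy differently by arm. That is possible, since YOCAS lasts 4 weeks and CBT-I lasts 8, but nothing in the documents shows it.

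**Working it through.** **Inputs.** SD 4.6, baseline–post correlation 0.576, margin 1.15, 168 evaluable per arm and alpha 0.025 (Sections 10.1 and 10.2.1); one-sided for non-inferiority (10.7.1).

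**The plan's own figure.**

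- Residual SD = 4.6 × √(1 − 0.576²) = 3.760
- SE = 3.760 × √(2/168) = 0.4103
- Interval half-width = 1.96 × 0.4103 = 0.804 ISI points
- Power = Φ(1.15/0.4103 − 1.96) = 80.04%

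The stated 80% is reproduced from a model with baseline ISI alone.

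**Effect of the omitted factor.** Let R² be the share of residual ISI variance that hormone therapy explains. The documents give no value, so 0%, 1%, 2% and 5% are assumptions. Put k = √(1 − R²).

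- Adjusted power = Φ(1.15/(0.4103k) − 1.96)
- Power with the factor balanced but omitted = Φ((1.15/0.4103 − 1.96)/k)
- One-sided type I error with the factor omitted = Φ(−1.96/k)
- Adjusted half-width = 0.804k

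| Assumed R² | Power, adjusted | Power, omitted | Gain (points) | Half-width, adjusted | Type I error, omitted |
|---|---|---|---|---|---|
| 0% | 80.04% | 80.04% | 0 | 0.804 | 0.0250 |
| 1% | 80.43% | 80.16% | 0.3 | 0.800 | 0.0244 |
| 2% | 80.82% | 80.28% | 0.5 | 0.796 | 0.0239 |
| 5% | 82.01% | 80.65% | 1.4 | 0.784 | 0.0222 |

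**Allowing for random loss.** The table assumes exact balance in the evaluable set. Keeping 168 of 240 per arm at random restores a fraction 1 − 168/240 = 0.30 of the imbalance variance that an unstratified trial would have. In the omitted-factor formulas k becomes √(1 − 0.7R²). Type I error is then 0.0246, 0.0242 and 0.0230 at R² of 1%, 2% and 5%. Omitted-factor power at 5% is Φ(0.843/√0.965) = 80.5%, so the gain there is about 1.6 points, not 1.4.

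**Superiority comparison.** At a true difference of 1.3 and two-sided alpha 0.025, adjusted power is Φ(1.3/(0.4103k) − 2.241) = 82.3%, 82.7%, 83.1% and 84.4%. With the factor balanced but omitted, Φ((1.3/0.4103 − 2.241)/k) gives 82.3%, 82.4%, 82.6% and 82.9%. The gains are of the same order as for non-inferiority.

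**Simulation.** With 8,000 trials per setting, 30% random loss and an assumed 50% prevalence of hormone therapy, power at R² = 5% was 80.6% omitted and 82.2% adjusted. Each simulated power has a standard error of √(0.8 × 0.2/8000) = 0.45 points. This is compatible with the formulas but too coarse to confirm gains of 0.3 to 0.5 points.

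**Unequal loss, as illustration only.** Assume 50% prevalence and a 10-point difference between arms in hormone therapy among completers. The hormone-therapy effect implied by R² is 3.760 × √(R²/0.25), so the unadjusted estimate moves by one tenth of that: 0.08, 0.11 or 0.17 ISI points at R² of 1%, 2% or 5%. The largest is about 15% of the margin (0.17/1.15), and the direction could be either way.

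**The case against.** The strongest reply is that nothing is wrong. Model and sample size agree with each other, type I error is controlled, power meets its target, and the continuous baseline score, the covariate most closely tied to the outcome, is already in. The size of any gain depends wholly on an assumed R²: it is nil at 0% and only 0.3 to 0.5 points at 1% to 2%. No decision is likely to turn on that. The exact-balance type I figures also overstate the conservatism once 30% are lost.

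Most of this stands. It fixes the weight of the point as a low-cost improvement, and the loss-corrected type I figures are the better ones. Aims 4 and 5 are exploratory and the gain there is slight. The unlisted imputation variables are a separate gap in detail and add no weight here.

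It does not remove the mismatch. The factor was important enough to stratify on, yet it is absent from the primary model without explanation. The exploratory list in 10.7.6 does not adjust any primary or secondary estimate. Nor do the moderator analyses mentioned in Section 7.1, which name no variable or model.

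**Conclusion.** The point holds as a minor one. Hormone therapy is a stratification factor that no primary or secondary model includes. The consequence is a slightly conservative test and a slightly wide interval. For R² between 0% and 5%, adjustment would add 0 to about 1.4 points of non-inferiority power (about 1.6 at the top if random loss is allowed for) and narrow the half-width from 0.804 to as little as 0.784, against a margin of 1.15. There is no inflation of false positives and no shortfall from the planned 80%. These sizes rest on the assumed R², an additive hormone-therapy effect, no site effect and loss that is random. The precision argument is worked out for the Aim 1 model; it carries over less directly to the later aims.

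**What to change.** In 10.7.1, add hormone therapy (yes/no, as recorded at randomisation) to the fixed effects, and carry it into 10.7.2 and 10.7.4. In 10.7.3, enter it together with its interaction with time: a main effect alone shifts all of a participant's time points equally and drops out of comparisons of change. Name it among the imputation variables in 10.6.2. The screening ISI stratum is optional, and matters mainly in Aims 2 and 4 if the outcome's own baseline replaces baseline ISI there. If the omission was deliberate, one sentence giving the reason would do instead.

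The cost is a sentence in 10.7.1, one in 10.6.2 and a short addition in 10.7.3. In each primary comparison of 336 evaluable participants (2 × 168), it uses about one of roughly 333 residual degrees of freedom (336 less intercept, group and baseline). It needs no new data and no more participants. Since 10.7.7 plans no interim efficacy analysis, the change can be pre-specified before any comparative results are seen.
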